13.6 Statistical Analysis

Summary statistics including mean, standard deviation, median, and range will be provided for continuous variables such as age, BMI, lab measurements, and scores from some HR-PRO measures of symptoms, and frequency count and percentage will be provided for categorical variables such as gender, response, toxicity type and severity.

To assess the primary endpoint (PFS), we will use the methods of Gooley et al.⁴⁴ to estimate the cumulative incidence of PFS “events”. A PFS event is defined as death or disease progression, including locoregional recurrence/progression or distant metastases. Time to PFS event is measured from treatment initiation until a recurrence, progression or occurrence or death, whichever occurs first.

Secondary endpoints include local-regional control, locoregional failure-free survival (LFFS), distant metastases (DM), DM free survival (DMFS) and overall survival (OS). Local failure is defined as failure (recurrence or progression) within the prescribed radiation field, including failure within 2 cm of the radiation field. Local control is defined as absence of local failure. LFFS is defined as alive and free of local recurrence or progression. Time to an LFFS event is measured from treatment initiation until local failure or death from any cause, whichever occurs first. Similarly, time to a DMFS event is measured from treatment initiation until distant metastases or death from any cause, whichever occurs first. Finally, OS is measured from treatment initiation until time to death from any cause.

The student t-test or the Wilcoxon rank sum test will be used to compare continuous variables between patient groups. The chi-square test or the Fisher’s exact test will be applied to evaluate the association between two categorical variables. Logistic regression models will be used to evaluate the effects of the important patient clinical factors including treatment on PFS. The distribution of time-to-event endpoints will be estimated using the method of Kaplan and Meier. Comparison of time-to-event endpoints by important subgroups will be made using the log-rank test. Proportional hazards regression may be employed for multivariate analysis on time-to-event outcomes. PROs will be assessed at the completion of reirradiation, and subsequently every ± 3 -months until 24-months post reirradiation. Generalized linear models for the repeated measures analysis will be performed to assess the change in PROs overtime with important covariates including treatment in the models.

The Investigator is responsible for completing safety summary report, and submitting it to the IND Office Medical Affairs and Safety Group, for review and approval.

Lead in phase/phase I:

Toxicity summary will be submitted after the first eight evaluable patients’ complete 1 cycle of therapy.

Approval from IND office will be obtained before advancing to phase 2.

Phase II:

Toxicity summary will be submitted after first 3 evaluable patients’ complete 1 cycle of therapy and every 3 evaluable patients complete cycle 1 thereafter.

A copy of the cohort summary should be placed in the Investigator’s Regulatory Binder under “sponsor correspondence”.

13.7

Subject Identification and Privacy

A unique number will be assigned to each subject, immediately after informed consent has been obtained. This number will serve as the subject's identifier in the trial as well as in the clinical trial database. All subject data collected in the trial will be stored under the appropriate subject number. Only the Investigators will be able to link trial data to an individual subject via an identification list kept at the site. For each subject, original medical data will be accessible for the purposes of source data verification by the Monitor, audits and regulatory inspections, but patient confidentiality will be strictly maintained.

Data protection and privacy regulations will be observed in capturing, forwarding, processing, and storing subject data. Subjects will be informed accordingly, and will be requested to give their consent on data handling procedures in accordance with national regulations.

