Unknown etiology, suspect possible bleeding	Consider blood transfusion at clinical discretion. Consider surgical/interventional radiology consultation. Consider imaging, as clinically indicated (e.g. FAST scan, CT scan, MRI, angiography). Consider endoscopy (upper/lower).
Unknown etiology despite above work-up	Hematology consultation. Consider bone marrow aspiration/morphologic evaluation.
ANC = absolute neutrophil count, Hgb = hemoglobin, CBC = complete blood count, INR = international normalized ratio, LDH = lactate dehydrogenase, LFT = liver function test, MCV = mean corpuscular volume, PT = prothrombin time, PTT = partial thromboplastin time, RDW = red cell distribution width, TIBC = total Iron binding capacity, and TSH = thyroid stimulating- hormone.	

Anemia severity reporting will follow the NCI-CTCAE v5 guidelines as below (

Table 4).

Table 4 Common Terminology Criteria for Adverse Events (CTCAE) Guidelines for Anemia Severity

CTCAE v.5	Grade 1	Grade 2	Grade 3	Grade 4
Anemia Hgb	Hgb < LLN-10.0 g/dL; < LLN-6.2 mmol/L; < LLN-100 g/L	Hgb < LLN-10.0-8g/dL; < LLN-6.2-4.9 mmol/L; < LLN-100-80 g/L	Hgb < LLN-8.0g/dL; < LLN-4.9 mmol/L; < LLN-80 g/L; transfusion indicated	Life-threatening consequences; urgent intervention indicated

Hgb = hemoglobin and LLN = lower limit of normal.
Signs and symptoms of anemia may include pallor of the skin and mucous membranes, shortness of breath, palpitations of the heart, soft systolic murmurs, lethargy, and fatigability.

Alterations in Wound Healing or Repair of Tissue Damage

Alterations of wound healing and tissue damage repair are considered a potential, theoretical risk for M7824 given TGF- β role in wound healing. Management should be discussed with the Medical Monitor for participants requiring surgery on study. Post-operative wound healing will be closely monitored.

Management should be discussed with the Supporting company EMD Serono for participants requiring surgery on study.

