10.1 General Assessments

The safety profile of M7824 will be assessed through the recording, reporting, and analysis of baseline medical conditions, AEs, physical examination findings, including vital signs, laboratory tests, ECOG PS, and 12-lead electrocardiogram (ECG) recordings.

The AE reporting period for safety surveillance begins when the participant receives the first dose of the investigational agent and continues until last Safety Follow-up visit or before start of any anticancer therapy, whatever comes first.

The safety assessments will be performed according to the Schedule of Assessments in Table 1.

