10.2 Adverse Drug Reactions Requiring Treatment Modification

Clinical Laboratory Assessments

It is essential that the Supporting company EMD Serono or designee be provided with a list of laboratory normal ranges before shipment of study drug. Any change in laboratory normal ranges during the study will additionally be forwarded to the CRO and the Supporting company EMD Serono.

All routine laboratory analyses will be performed at a laboratory facility local to the study site, and relevant results must be available and checked before administration of treatment (details to be provided in the Laboratory Manual).

If a participant has a clinically significant abnormal laboratory test value that is not present at baseline, the test should be closely monitored until the test value has returned to the normal range or the Investigator has determined that the abnormality is chronic or stable.

The report of the results must be retained as a part of the participant's medical record or source documents.

Abnormal laboratory findings and other abnormal investigational findings (eg, on an ECG trace) should not be reported as AEs unless they are associated with clinical signs and symptoms, lead to treatment discontinuation, or are considered otherwise medically important by the Investigator. If a laboratory abnormality fulfills these criteria, the identified medical condition (eg, anemia, increased ALT) must be reported as the AE rather than the abnormal value itself.

See the Schedule of Assessments in Table 1 for further details.

Specific Planned Assessments or Adverse Events of Special Interest

AESIs are serious or non-serious AEs specific to known mechanism of action of the treatment drug that are of clinical interest requiring ongoing monitoring and rapid communication for optimal on-time management.

IRRs, including immediate hypersensitivity

Any signs or symptoms experienced by participants during the infusion or any event occurring during or within one day of drug administration should be evaluated as potential IRRs. IRRs are common ADRs with monoclonal antibodies (mAbs) timely related to drug administration and have been reported as anaphylaxis, anaphylactoid reactions and cytokine release syndrome, among other terms used. IRRs are an AESI for M7824, and important identified risks (adverse reactions) for M7824, the precautions and management are discussed in Section 0.

Immune-related adverse events (irAEs)

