Immune-related AEs are defined as off target side effects associated with exposure of an immunogenic drug and are consistent with an immune mechanism. In the process of identification of irAEs, any possible etiology of neoplastic, infectious, metabolic, toxin, or any other factor should be ruled out. Serologic, histologic (biopsy), and/or immunologic results should be obtained to evaluate the differential diagnosis and/or support an immune-mediated cause. Immune-related AEs are AESIs for M7824 and important identified risks for M7824, the precautions and management are discussed in Section 0.

Skin adverse events

Skin AEs are AESIs for M7824, and include 2 potential mechanisms:

1. Skin AEs possibly due to TGF- β inhibition: rash with hyperkeratosis, KA, and SCC. Skin lesions with hyperkeratoses, keratoacanthoma, cSCC possibly due to TGF- β inhibition are identified risks for M7824. For more information, see Section 0.

Treatment-related skin lesions with hyperkeratosis, KA, cSCC possibly due to TGF- β inhibition were reclassified as important identified risks (adverse reactions) at the end of the safety reporting period of July 2017; however, they have been manageable and did not lead to permanent discontinuations in Studies EMR200647-001/EMR200647-008.

2. Immune-related skin AEs (irAEs) possibly mediated by PD-L1 inhibition (events in this category are also reported under irAEs). For more information, see Section 0.

Treatment-related anemia adverse events

Anemia is considered a potential risk based on toxicological findings with M7824 in the cynomolgus monkey indicating a decrease in Hgb, red blood cells (RBCs), and hematocrit that was fully reversible or showed a substantial trend toward recovery. Treatment-related anemia AEs are AESIs for M7824. A consistent clinical risk of treatment-related anemia on M7824 was not observed in Study EMR200647-001. As summarized in the Investigator Brochure, treatment-related anemia was reported in 6.1% (n=23)

of the participants from a number of cohorts. For more information, see Section 0 and refer to the Investigator Brochure.

Alterations in wound healing or repair of tissue damage

Due to the involvement of TGF- β in repair of skin and other tissue injuries, alterations in wound healing or repair of tissue damage is considered a potential risk. No AEs have been reported in Phase I studies. For any surgeries conducted post-treatment initiation, surgical wound healing will be closely monitored.

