12. ADVERSE EVENTS

The investigator is required to report to the supporting company EMD Serono or its representative all AEs occurring during the clinical study (Title 21 Code of Federal Regulations [CFR] Part 312.64[b] and International Conference on Harmonization [ICH] E6 [R2]).

At each study visit, subjects will be evaluated for new Adverse Events (AE) and the status of existing AEs. All AEs observed from the date of the first administration of study treatment until the end of the follow-up period of the study (study cut-off date) are to be recorded on the AE page of the e-CRF. The date of onset and resolution, determination of seriousness, severity, grade, corrective treatment, outcome, and relationship to study treatment (M7824, Radiotherapy) will be recorded for all AEs.

All Serious Adverse Events (SAEs) occurring from the date of onset of the study treatment until the end of follow-up period of the study (study cut-off date) will be collected.

This study will utilize the NCI Common Terminology Criteria for Adverse Events (CTCAE) version 5.0 for adverse event (AE) reporting. The CTCAE version 5.0 is located on the CTEP website at http://ctep.cancer.gov/protocolDevelopment/electronic_applications/ctc.htm.

An Adverse Event is defined as any untoward medical occurrence in a patient regardless of its causal relationship to study treatment. An AE can be any unfavorable and unintended sign (including any clinically significant abnormal laboratory test result), symptom, or disease temporally associated with the use of the study treatment, whether or not it is considered to be study drug(s) related. Included in

this definition are any newly occurring events and any previous condition that has increased in severity or frequency since the administration of study therapy.

The investigator (or physician designee) is responsible for verifying and providing source documentation for all adverse events and assigning the attribution for all adverse events for subjects enrolled.

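### Laboratory results are summarized only as continuous variables, so CTCAE-gradable changes not filed as adverse events are never counted by grade

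*Combined protocol and SAP*

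**What the plan says.** Section 10.1 makes laboratory tests part of the safety assessment, which rests on "recording, reporting, and analysis of baseline medical conditions, AEs, physical examination findings, including vital signs, laboratory tests". The only method of analysis stated for them is in Section 13.6: "Summary statistics including mean, standard deviation, median, and range will be provided for continuous variables such as age, BMI, lab measurements". The same paragraph sets out the categorical summaries: "frequency count and percentage will be provided for categorical variables such as gender, response, toxicity type and severity".

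Whether a laboratory change reaches the toxicity counts depends on the adverse event rules. Section 10.2 says of abnormal findings that they "should not be reported as AEs unless they are associated with clinical signs and symptoms, lead to treatment discontinuation, or are considered otherwise medically important"; that last judgment is left to the investigator. Section 12 includes in its adverse event definition "any clinically significant abnormal laboratory test result", applies CTCAE v5.0 to adverse event reporting, and leaves grading to the treating physician.

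Some laboratory changes have a route of their own. Section 10.2 states "Immune-related AEs are AESIs for M7824 and important identified risks for M7824" and "Treatment-related anemia AEs are AESIs for M7824". For hemoglobin, Section 6.2.3 adds "Anemia severity reporting will follow the NCI-CTCAE v5 guidelines as below", followed by the cut-offs in Table 4.

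**The concern.** A laboratory change that can be graded but is not filed as an adverse event is absent from the toxicity counts. It then survives only inside a mean, SD, median and range, and none of these says how many patients reached a given grade. For such changes, any per-patient count depends on individual filing decisions.

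The tests concerned matter for this drug. Section 2.5 names lipase increase, ALT increase, anemia and acute kidney injury among the grade 3 or higher events seen in 377 patients, and one patient had a grade 4 lipase increase. Acute and late toxicity by CTCAE v5.0 is a secondary endpoint (Section 13.4).

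A continuous summary also does not separate new change from abnormality present at entry. Section 3.1 admits patients with hemoglobin from 9.0 g/dL, while Table 4 puts 8 to 10 g/dL at grade 2, so a patient can already be at grade 2 on enrollment.

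**Working it through.** The plan gives no figure to reproduce. The check has three parts: where each kind of laboratory change ends up, whether the planned statistics could replace a count by grade, and how much data are already scheduled.

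**1. Where a laboratory change ends up**

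| Kind of change | Filed as an adverse event? | Counted by grade under 13.6? |
|---|---|---|
| Symptomatic, or leading to discontinuation | Yes (10.2) | Yes |
| Clinically significant or judged medically important | Yes (10.2, 12) | Yes |
| Immune-related event, treatment-related anemia | Yes, as an event of special interest (10.2) | Yes |
| Gradable, but none of the above | No (10.2) | No |

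Only the last row is a gap. The protocol foresees values of this kind: the grade 4 rule in Section 6.2.3 exempts isolated out-of-range laboratory values without clinical relevance from permanent discontinuation. No section plans a worst-grade table or a shift table from recorded values. The Table 4 cut-offs serve anemia severity reporting and are not tied to a tabulation.

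**2. Do the planned statistics fix the count by grade?**

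Two sets of hemoglobin values (g/dL) were constructed with N = 21, the phase II sample size in Section 13.5.

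- Set A: 8.2, 9.1, 10.0, 10.0, 10.1, 10.3, 10.5, 11.1, 11.4, 11.8, 11.8, 12.2, 12.2, 12.4, 12.9, 13.1, 13.7, 13.7, 14.3, 14.5, 14.8
- Set B: 8.2, 9.3, 9.4, 9.9, 9.9, 10.2, 11.3, 11.6, 11.6, 11.7, 11.8, 12.1, 12.2, 12.3, 12.6, 13.1, 13.3, 14.0, 14.3, 14.5, 14.8

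The sum (248.1) and sum of squares (2998.67) are the same in both. Hence, for each set:

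- mean = 248.1 / 21 = 11.814
- SD = √[(2998.67 − 248.1² / 21) / 20] = √(67.546 / 20) = 1.838
- median = 11.8; range = 8.2 to 14.8

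Counts at grade 2:

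| Reading of the boundary | Set A | Set B |
|---|---|---|
| 8 to <10.0 g/dL | 2/21 (9.5%) | 5/21 (23.8%) |
| 10.0 g/dL also counted as grade 2 | 4/21 (19.0%) | 5/21 (23.8%) |

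Table 4 prints 10.0 in both the grade 1 and grade 2 cells, so both readings are shown. On either one, identical planned summaries go with different counts. The values are artificial and estimate no rate.

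**3. What is already collected**

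From Table 1, for a patient on full treatment:

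- Chemistry, blood count and liver panels: 1 screening + 12 cycles × 2 visits + 1 at the 90-day visit = 26, or up to 26 × 21 = 546 for 21 patients.
- Lipase and amylase, every other cycle, assuming one draw in each such cycle: 1 + 6 + 1 = 8, or up to 8 × 21 = 168.

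**The case against.** The strongest reply is that this is a preference rather than an error. Section 13.6 is a short descriptive paragraph with open-ended lists, nothing in it forbids a graded table, and Section 10.1 prescribes no format. What remains uncounted is narrow and was set aside on purpose: changes that cause no symptoms, do not stop treatment and are not judged important. Filed events already separate new from pre-existing abnormality, because Section 12 counts only new events and worsening of existing conditions. The planned range also shows the extremes: a minimum of 8.2 g/dL means that no value in that summary is at grade 3 (below 8.0).

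The numerical example is open to criticism too. That a mean and SD do not fix counts in bins is true of any variable. The example uses hemoglobin, for which treatment-related anemia would be filed. With 10.0 g/dL counted as grade 2, the contrast shrinks to 4 against 5.

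Most of this stands, and it limits the weight of the point. It does not remove it. Permission to run an analysis is not a plan to run it, and laboratory data are explicitly placed in the continuous group. The range shows the worst value, but not how many patients came near it.

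A last objection is that Section 10.2 keeps result reports in source documents and no text says every value is entered in the case report form. Section 13.6 already commits to summarizing laboratory measurements, however, so the values have to be available for analysis.

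**Conclusion.** The point holds as a cheap, optional improvement at the lowest severity. As written, the plan gives no count of patients by CTCAE grade for laboratory changes that are gradable but not filed. For those changes, the planned continuous statistics cannot supply one.

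The size of the gap cannot be estimated, because the documents give no rate of unfiled changes. The contrast of 2 against 5 patients in 21 (4 against 5 on the other boundary reading) shows only that the planned summary leaves the count undetermined. The conclusion assumes that the filing rule in Section 10.2 is followed and that the toxicity counts in 13.6 are drawn from filed events.

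Sample size, power, the DLT rule, the primary endpoint and patient monitoring are unaffected. Section 10.2 still requires relevant results to be checked before each dose.

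**What to change.** Add one sentence to Section 13.6, keeping the continuous summaries: for each CTCAE-gradable laboratory test already in Table 1, report the number and percentage of patients by worst post-baseline CTCAE v5.0 grade against baseline grade. Derive the grades from recorded values, from first dose to the first follow-up visit 90 days after the last dose, whether or not an adverse event was filed. Also state which grade a hemoglobin of exactly 10.0 g/dL receives.

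The cost is that sentence, one more table and the programming of grades. No new sampling is needed. Rates in the table will be somewhat above those in the adverse event listing, so it needs a footnote saying that it counts values regardless of filing. Fixing the tests and cut-offs in advance also prevents their being chosen after the data are seen.

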2.3 Stereotactic Radiotherapy

Modern highly conformal radiotherapy techniques, such as intensity modulated radiation therapy (IMRT), proton therapy, and SBRT are attractive options for those with recurrent HNSCC. Retrospective and prospective reports have demonstrated improved local disease control and survival compared with use of 2D and 3D radiotherapy³⁴⁻³⁶. Our institution recently published the largest series of 207 patients reirradiated with IMRT with curative intent. The 2-year LRC and overall survival (OS) rates were 65% and 57%, and 5-year rates were 49% and 42%, respectively⁹. The median survival was 25.1 months overall and 22.5 months for patients with SCC histology. The grade 3 or higher treatment related morbidity was 32% at 2 years and 48% at 5 years. Multivariate analysis showed that retreatment volume >50 cc (P=0.001) and use of platinum based chemotherapy (P=0.02) were associated with higher late grade 3 toxicity rates⁹. Similarly, our recently published study of 60 patients reirradiated with proton beam showed 2 year LRC and OS rates of 73% and 70%, respectively. The 2 year late grade 3 or higher toxicity rate was 26%¹⁰.

SBRT enables precise and focused delivery of ablative dose radiation in a limited number of treatments (typically 1-5) and has become a standard approach in several disease sites such as lungs, brain and prostate³⁷⁻⁴¹. Logistical and financial advantages of SBRT over existing conformal radiotherapy modalities include fewer number of treatments, shorter treatment duration (typically <2 weeks vs 6-7

weeks), fewer clinic visits and/or lost work hours. Clinical advantages of SBRT include reduced exposure of nearby normal tissues to reirradiation dose, use of ablative/high doses to confer additional mechanisms of cell kill, superior immune elicitation compared with standard fractionation, and a shorter interval to systemic therapy that benefits a population at high risk for metastatic development⁴².

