A growing body of literature demonstrates SBRT for HNSCC reirradiation can provide durable local-regional control and is well tolerated relative to conventionally fractionated RT^{37-41 29-30}. Retrospective and prospective studies from the University of Pittsburgh and others demonstrate SBRT is associated with late grade 3 toxicity rates between 10% and 30% when delivered with every other day (QOD) frequency. The 2-year local control rates were 35-65% and 1-year OS rates were 30-60%^{43,44 41,45,46}. Our recently reviewed institutional experience of 101 patients with recurrent HNSCC reirradiated with SBRT to a median dose of 45 Gy in 5 fractions (delivered QOD) showed a 1-year local control rate of 87%, with a median follow-up of 15.9 months (unpublished data). Patient reported quality of life outcomes showed lower symptom burden associated with SBRT⁴⁷. No difference in disease control rate or progression free survival for recurrent versus second primary tumors in a previously radiated field was noted on our institutional data, which is consistent with other published experiences^{9,48,49}.

Although local control with SBRT reirradiation is promising, recurrences outside the reirradiation field remains problematic. Our data demonstrates 1- and 2- year regional recurrence rates of 16% and 24%, respectively, and 1- and 2-year distant recurrence rates of 16% and 28%, respectively (manuscript in progress). Furthermore, head and neck reirradiation is associated with severe, long-term treatment related adverse events, with rates of severe fibrosis/dysphagia as high as 40%^{7,8}. Even with the use of conformal IMRT and proton radiotherapy, 2-year grade 3 or higher toxicity rates approaches 30%^{9,10}.

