Serious Adverse Events (SAEs) will be reported within 24 hours of acknowledge by the study team, unless it occurs over the weekend or holidays, when it will be notified in the first business day. They are defined as any adverse drug event (experience) occurring at any dose that results in any of the following outcomes: death; a life-threatening adverse drug experience; inpatient hospitalization or prolongation of existing hospitalization; a persistent or significant disability/incapacity; a congenital anomaly/birth defect. Important medical events that may not result in death, be life threatening, or require hospitalization may be considered an SAE, when, based upon medical judgment, they may jeopardize the patient and may require medical or surgical intervention to prevent one of the outcomes listed in the definition.

Toxicities will be assessed by the treating physician/s according to the CT Cv5 criteria.

Early onset (acute) toxicities occurring prior to 90 days will also be considered late onset (chronic) toxicities if they persist for at least one day beyond the 90 days used to define late onset (chronic) toxicities. In analyses that examine acute and chronic toxicities separately, those toxicities that began as acute but became chronic will be included in both the analysis of acute toxicities and in the analysis of chronic toxicities.

Immune-related AEs should be documented as an 'Adverse Event of Special Interest (AESI)', and it is recommended to involve the Medical Monitor at first incidence and subsequently as needed for follow up. Details of the diagnostic work up will be requested by the study team. Immune-related AEs are described in Section 0.

For reporting irAE severity/toxicity grading, refer to NCI-CTCAE v.5 toxicity grading system.

Toxicities related to radiation therapy include: Pain, mucositis, constipation, dysphagia, odynophagia, hemoptysis, epistaxis, trismus, fatigue, weight loss, dysgeusia, nausea, radiation dermatitis, myelosuppression, skin erythema, subcutaneous fibrosis, esophagitis, myelitis, superficial soft tissue fibrosis and esophageal stricture.

Toxicities related to IO therapy are described in detail in the investigator's brochure.

Toxicity monitoring: Both Acute (From radiation start to 90 days after completion of radiation therapy) and Late (90 days to 2 years from the completion of radiation therapy) side effects of radiation therapy will be documented and graded according to the NCI-CTCAE version 5.0.

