13.5 Sample Size

The statistical considerations for the Phase I/II design are described as follows:

This is a phase I/II, open label, single arm study to evaluate M7824 plus SBRT in patients with locoregional recurrent HNSCC after prior head and neck radiotherapy that are not good candidates for salvage surgery (Figure 1). Patients must have evaluable disease by RECIST or RECIST 1:1 and a performance status ECOG 0-2. Time elapsed from prior radiotherapy must be at least 6 months.

Sample Size

In the phase I portion, 8 patients will be enrolled to access safety and toxicity. The primary endpoint is dose-limiting toxicity (DLT) defined as M7824 related \geq grade 3 adverse event (AE) unresolved to \leq grade 1 in \leq 28 days, or incomplete SBRT. DLT window is from first M7824 dose (D0) until 14 days post SBRT (D28). More than 2 DLTs in 8 evaluable patients will be considered unacceptable.

In the phase II portion, the primary endpoint is PFS at 1 year. Based on the prior studies [unpublished data from MD Anderson], we assume that the one-year PFS of the standard treatment is 0.60. If the new treatment improves the one-year PFS to 0.80 or higher, it will be considered a clinically important improvement. A sample size of 21 patients (with 1.5-year additional follow-up after the last patient is enrolled) will allow us to observe an improvement in 1-year PFS from 0.60 to 0.80. This will enable the study 80% power to detect the specified difference in PFS. Power was calculated using a log-rank test with a one-sided type 1 error rate of 0.10 (EAST 5.4 and STPLAN version 4.5). Based on our estimated accrual rate of 2 patients per month, we expect enrollment to be completed in 11 months. The total study duration is 29 months.

DMI (Data Management Initiative) database

Clinical data capture called DMI (Data Management Initiative) and CORe will be the electronic database used for this study's electronic case report forms.

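### Late toxicity has a 2-year window but is reported only as a count and percentage, so patients with short follow-up count as event-free and the result falls below the 2-year cumulative incidence

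*Combined protocol and SAP*

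**What the plan says.** Acute and late toxicity, and fibrosis-related toxicity, are secondary endpoints (Sections 1.3 and 13.4). Section 12 sets the window: "Late (90 days to 2 years from the completion of radiation therapy) side effects of radiation therapy will be documented and graded". It also counts an acute toxicity as late if it lasts past day 90.

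The one analysis sentence in Section 13.6 that names toxicity reads "frequency count and percentage will be provided for categorical variables such as gender, response, toxicity type and severity". The same section plans "to estimate the cumulative incidence of PFS" events and adds that "The distribution of time-to-event endpoints will be estimated using the method of Kaplan and Meier". It defines its time-to-event endpoints (PFS, LFFS, DMFS, OS and related measures), and toxicity is not among them.

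The documents disagree on how long toxicity is observed:
- Section 13.5: 21 patients, "with 1.5-year additional follow-up after the last patient is enrolled", 29 months in total.
- Section 8.4: the study ends one year after the last participant's last dose.
- Section 10.1: adverse-event reporting ends at the last safety follow-up visit or at new anticancer therapy.
- Section 12: recording runs to study cut-off, and late effects are graded to 2 years.
- Table 1: adverse-event evaluation is marked up to the first follow-up visit, 90 days after the last dose, but not in the column for years 2 to 5.

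Section 2.3 quotes time-based rates. For IMRT, "The grade 3 or higher treatment related morbidity was 32% at 2 years and 48% at 5 years"; for protons, 26% at 2 years; for both, "2-year grade 3 or higher toxicity rates approaches 30" per cent. For SBRT it gives 10 to 30% with no time point.

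**The concern.** A percentage of all treated patients describes a 2-year window only if everyone is observed to the end of that window, to an event, or to death. A patient censored at 17 months without an event adds a full unit to the denominator, as if known to be event-free at 24 months. The error can only lower the rate.

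Reducing radiation fibrosis is a stated reason for using M7824 (Section 2, and again in Section 2.6), so a low late-toxicity figure is a result that readers will look for. If the figure partly reflects how long patients were watched, it cannot be interpreted without knowing that time.

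**Working it through.** **The plan's own figures.** No expected rate, sample size or power is stated for late toxicity. The Section 13.5 timeline reproduces: 21 / 2 per month = 10.5, stated as 11 months; 11 + 18 = 29 months.

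**Step 1: who can be followed for 24 months after radiotherapy.** SBRT starts two weeks after the first dose (13.2) and takes two weeks (6.1.3), so it ends at about month 1. The DLT window in 13.2 instead puts 14 days after SBRT at D28, so about month 0.5. With uniform entry over 11 months:
- Cut-off at 29 months: (29 − 24 − 1)/11 = 36% (7.6 of 21) to (29 − 24 − 0.5)/11 = 41% (8.6 of 21), before any death or loss.
- Section 8.4: the last dose of twelve 28-day cycles falls 11 × 28 + 14 = 322 days (10.6 months) after the first. The cut-off is 11 + 10.6 + 12 = 33.6 months, and the share is 78 to 83%.

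**Step 2: size of the shortfall.** Assumptions, not in the documents: no drug effect; a 2-year rate of 30% with deaths censored (1 − Kaplan-Meier); constant toxicity hazard from month 3 to month 24 after radiotherapy; independent exponential death; radiotherapy ending at month 1; no loss to follow-up; all treated patients in the denominator.

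Toxicity hazard h = −ln(0.70)/21 = 0.01698 per month. With death hazard μ per month, the probability of an observed event by T months after radiotherapy (3 ≤ T ≤ 24) is

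F(T) = exp(−4μ) × h/(h+μ) × [1 − exp(−(h+μ)(T−3))].

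- The 2-year cumulative incidence is F(24).
- The crude rate at the 29-month cut-off averages F(min(U, 24)) over U uniform on 17 to 28 months.
- If evaluation stops at the last marked Table 1 visit: 322 + 90 = 412 days = 13.5 months after first dose, so the crude rate is F(12.5).

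Example, 1-year OS 60%: μ = −ln(0.60)/12 = 0.04257; F(24) = 0.843 × 0.285 × 0.714 = 0.172.

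| Survival assumed | F(24) | Crude, 29 months | Gap (points) | Crude, Table 1 visit | Gap (points) |
|---|---|---|---|---|---|
| No deaths | 0.300 | 0.272 | 2.8 | 0.150 | 15.0 |
| 2-year OS 70% (proton, 2.3) | 0.245 | 0.225 | 2.0 | 0.132 | 11.3 |
| 2-year OS 57% (IMRT, 2.3) | 0.219 | 0.203 | 1.6 | 0.122 | 9.7 |
| 1-year OS 80% (assumed) | 0.233 | 0.215 | 1.8 | 0.128 | 10.6 |
| 1-year OS 60% (top of SBRT range, 2.3) | 0.172 | 0.161 | 1.1 | 0.104 | 6.7 |

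If the Table 1 visit falls at the end of its 14-day window and radiotherapy ends at month 0.5, T is about 13.5. F(13.5) at 1-year OS 60% is 0.112, a gap of 6.0. Under the Section 8.4 cut-off the gaps are 0.1 to 0.3 points.

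**Step 3: what deaths do.** The distance from 0.30 to F(24) is 5.5 points (2-year OS 70%) to 12.8 points (1-year OS 60%). That is a difference between two estimands, and it remains after the fix. Adding the follow-up gap puts the crude rate at 0.225 to 0.161, about 16 to 23% against 30%. At 1-year OS 60%, 12.8 of the 13.9 points come from the estimand and 1.1 from short follow-up.

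**Step 4: precision.** One patient in 21 is 4.8 points. The exact 95% interval for 4/21 is 5 to 42%. The chance of 3 or fewer events in 21 is 0.086 at a rate of 0.30, 0.25 at 0.23 and 0.33 at 0.21.

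**The case against.** The strongest reply is that cumulative incidence moves the estimate by only 1 to 3 points when adverse events are collected to the 29-month cut-off. That is less than one patient in 21, in a descriptive secondary endpoint. With complete follow-up, the crude percentage and the cumulative incidence coincide. This stands, and it limits the point to a modest one unless collection stops early.

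A reader might infer something stronger: that the plan will make M7824 look anti-fibrotic, by 8 to 14 points against historical rates near 30%. The documents do not support that, for these reasons:
- The large gap requires the historical 26% and 32% to be estimates that censor deaths. Section 2.3 does not say how they were obtained. If they are cumulative incidences, only the small follow-up gap remains.
- No toxicity comparison with historical rates is planned. QALY is the only stated historical contrast.
- The time-based benchmarks are for IMRT and protons. The SBRT range of 10 to 30% has no time point and already contains 16 to 23%.
- Fibrosis is also assessed by HN-LEF, CROM, DIGEST and LSIDS-HN, so the adverse-event table is not the only evidence.
- Counting persistent acute events as late raises the count.

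Two other defences are weaker. Section 13.6 states no denominator, so the all-treated one is an assumption; but a plan that leaves it open still needs to state it. And the general Kaplan-Meier sentence does not cover late toxicity, which is not defined as a time-to-event endpoint. Applying it would treat deaths as censored.

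**Conclusion.** The point holds in a limited form. The stated analysis does not match a 2-year window in which about 60% of patients cannot be observed to the end under Section 13.5. On an all-treated denominator the percentage understates the 2-year cumulative incidence by about 1 to 3 points under that section and by almost nothing under Section 8.4. The shortfall is about 6 to 11 points, with deaths at the survival rates shown, if evaluation ends at the last marked Table 1 visit. The collection rules therefore matter more than the choice of estimator. Stopping at new anticancer therapy (Section 10.1) would also lower the rate. It is not quantified here because the rate of new therapy is not stated, and such stopping may be informative.

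These sizes rest on the 30% rate, exponential times, independent death and no loss to follow-up. Any loss would lower the crude rate further. A no-effect drug showing 16 to 23% against 30% is possible only if the historical rates censor deaths, which the documents leave open. The primary endpoint is unaffected.

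**What to change.** In Section 13.6, report late grade 3 or higher toxicity as cumulative incidence at 1 and 2 years after radiotherapy. Treat death as a competing event, censor at the last adverse-event assessment, and give numbers at risk and confidence intervals. Keep counts and percentages as a supplementary table with a stated denominator. State that an acute event persisting past day 90 enters as a late event at day 90, in line with Section 12.

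Reconcile Table 1 and Sections 8.4, 10.1, 12 and 13.5 so that toxicity is assessed through the 2-year window; no estimator recovers events that were never collected. Label any comparison with historical rates descriptive, and use the estimator that produced the historical figure.

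Cost: SAP wording and one further analysis. Onset and resolution dates are already to be recorded under Section 12, but closing the Table 1 gap means some added adverse-event assessment at late visits. No extra patients are needed, and intervals will be wide with 21.
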